9.10 OTHERS ASPECTS

None.

10 PROTECTION OF HUMAN SUBJECTS

10.1 RESPONSIBILITIES OF THE INVESTIGATOR /HEALTH CARE PROVIDERS

The Investigator/Health Care Provider will perform the study in accordance with this protocol, applicable local regulations and international guidelines.

It is the Investigator /Health Care Provider's responsibility to obtain written informed consent from patients prior to inclusion in the study, to fill in the CRF and to record all data pertinent to the investigation. She/he will ensure that the information reported in the CRF is precise and accurate.

Investigator /Health Care Provider, and under the Health Care Provider's responsibility, should fully inform the Patient of all pertinent aspects of the study including the written information. All patients should be informed to the fullest extent possible about the study, in language and terms they are able to understand.

Prior to a patient's participation in the study, the written Informed Consent Form should be signed, name filled in and personally dated by the patient or by the patient's legally acceptable representative, and by the person who conducted the informed consent discussion. A copy of the signed and dated written Informed Consent Form will be provided to the patient.

The Informed Consent Form and the Information Sheet used by the Investigator/Health Care Provider for obtaining the Patient's Informed Consent must be reviewed and approved by the MAH/MAH representative prior to submission to the appropriate Independent Review Board/Ethics Committee (IRB/IEC) for approval/favorable opinion.

10.2 RESPONSIBILITIES OF MAH/MAH REPRESENTATIVE

The MAH/MAH representative is responsible for taking all reasonable steps and providing adequate resources to ensure the proper conduct of the study.

MAH/MAH representative is responsible for:

- Local submission(s) complying with data protection rules,
- Any other local submission(s).

10.3 ETHICAL, REGULATORY AND ADMINISTRATIVE RULES

10.3.1 Ethical principles

This study will be conducted in accordance with the principles laid by the 18th World Medical Assembly (Helsinki, 1964) and all subsequent amendments.

Property of the Sanofi Group - strictly confidential

10.3.2 Laws and regulations

This study will be conducted in accordance with the guidelines for Good Epidemiology Practice (GEP) (13).

Each participating country should locally ensure all necessary regulatory submissions (e.g., IRB/IEC) are performed in accordance with local regulations including local data protection regulations.

10.3.3 Data protection

The women's, infants', and their HCPs' personal data which may be included in the MAH/MAH representative study database shall be treated in compliance with all local applicable laws and regulations.

When archiving or processing personal data pertaining to the women, infants, and HCPs, MAH/MAH representative shall take all appropriate measures to safeguard and prevent access to this data by any unauthorized third party.

10.3.4 Insurance

Participating countries may contract insurance according to local specific requirements.

10.3.5 Secrecy agreement

All material, information (oral or written) and unpublished documentation provided to any third parties involved with the conduct of the study (or any action carried out by the MAH/MAH representative on their behalf), including the present protocol and the CRF, are exclusive property of the MAH/MAH representative.

These materials or information (both global and partial) cannot be given or disclosed by any third parties to unauthorized persons without the prior formal written consent of the MAH/MAH representative.

The National coordinator shall consider as confidential all the information received, acquired, or deduced during the study and will take all necessary steps to ensure that there is no break of confidentiality, other than for information to be disclosed by law.

10.3.6 Record retention

The Study Coordinating Center shall arrange for the retention of study documentation until the end of the study. In addition the Study Coordinating Center will comply with specific local regulations/recommendations with regards to record retention for women and their infants.

The Study Coordinating Center shall arrange for retention of the study documents at least 5 years after the completion or discontinuation of the study, unless otherwise specified in the Study Coordinating Center Agreement in line with additional standards and/or local laws.

Property of the Sanofi Group - strictly confidential

However, applicable regulatory requirements should be taken into account in the event that a longer period is required.

10.3.7 Discontinuation of the study

The MAH/MAH representative can decide at any time and for any reason to discontinue the study; the decision will be communicated in writing to the participating Investigator.

Similarly, should the Investigator decide to withdraw from the study, she/he will have to inform the MAH/MAH representative in writing.

If appropriate, according to local regulations, Ethic Committee(s) (IRB/IEC) and Competent Authorities should be informed.

10.3.8 MAH/MAH representative audits and inspections by competent authorities

The National coordinator involved with this study agree to allow the MAH/MAH representative auditors/Competent Authorities inspectors to have direct access to their study records for review, being understood that these personnel are bound by professional secrecy, and as such will not disclose any personal identity or personal medical information.

The National coordinator will make every effort to help with the performance of the audits and inspections, giving access to all necessary facilities, data, and documents. The confidentiality of the data verified and the protection of the patients should be respected during these inspections.

Any result and information arising from the inspections by the competent authorities will be communicated by third parties to the MAH/MAH representative.

The national coordinator involved with this study shall take appropriate measures required by the MAH/MAH representative to take corrective actions for all problems found during the audit or inspections.

11 MANAGEMENT AND REPORTING OF ADVERSE EVENTS/ADVERSE REACTIONS

Spanning from the signature of the informed consent form until the end of the study as defined by the protocol, all serious adverse events (SAEs), including medically important events and pregnancy outcome related events (see Section 11.1.1), and non-serious AEs which potentially impact pregnancy outcome, will be collected by the HCP, submitted to the National Coordinator and reported to the MAH/MAH representative within expedited time frame (see Section 11.1.2.2).

Pregnancy related events, occurring BEFORE the signature of the informed consent for each patient are to be reported as part of the Pregnancy History.

11.1 SAFETY INSTRUCTIONS

11.1.1 Definitions of Adverse Event (AE) and Serious Adverse Event (SAE)

An **Adverse Event (AE)** is any untoward medical occurrence or clinical investigation in a patient administered a pharmaceutical product and which does not necessarily have to have a causal relationship with this treatment.

A **Serious Adverse Event** is an adverse event that at any dose:

- Results in death or;
- Is life-threatening or;
- Requires inpatient hospitalization or prolongation of existing hospitalization or;
- Results in persistent or significant disability/incapacity or;
- Is a congenital anomaly/birth defect;
- Is a medically important event;
- Suspected transmission of infectious agent; is any suspected transmission of an infectious agent via a medicinal product (e.g., product contamination).

Note: The term "life-threatening" in the definition of "serious" refers to an event in which the patient was at risk of death at the time of the event; it does not refer to an event which hypothetically might have caused death if it were more severe.

For this study, SAEs also include specific pregnancy outcome related events: all spontaneous abortions, stillbirths, neonatal deaths, and foetal major malformations occurring in a LEMTRADA-exposed pregnancy.

Medical and scientific judgment should be exercised in deciding whether expedited reporting is appropriate in other situations, such as important medical events that may not be immediately life threatening or result in death or hospitalization but may jeopardize the patient or may require intervention to prevent one of the other outcomes listed in the definition above. Examples of such events may include, but are not limited to malignancies, events requiring intensive treatment in an emergency room or at home, as allergic bronchospasm or convulsions, that do not result in inpatient hospitalization.

The following events should be reported in the same fashion as SAEs (within 24 hours within becoming aware of the event) if seriousness criteria, including "medically important" are met: autoimmune mediated conditions, including immune thrombocytopenia; thyroid disorders; other non-thyroid autoimmune diseases as nephropathies (including anti-glomerular basement membrane (anti-GBM) disease), cytopenias; serious infections (including serious opportunistic infections); pneumonitis, malignancy and symptomatic overdose (serious or non-serious) with LEMTRADA.

11.1.2 Obligations of the Investigator regarding safety reporting

11.1.2.1 Adverse Events collection

- All SAEs, including medically important events and pregnancy outcome related events.
- All non-serious AEs which to the opinion of HCP or National Coordinator may have an impact on the outcome of the pregnancy whether causally related to drug product or not.

11.1.2.2 Adverse event reporting to MAH/MAH REPRESENTATIVE

• In case of Serious Adverse Events

The National Coordinator will report to MAH/MAH representative Safety within 24 hours of becoming aware of an SAE, including medically important events and pregnancy outcome related events.

• In case of Non Serious Adverse Events with potential impact on pregnancy outcome

Adverse events should be reported by National Coordinator to MAH/MAH representative as soon as possible, not later than within **30 days of awareness**.

11.2 SAFETY OBSERVATIONS

- The Investigator should take all appropriate measures to ensure the safety of the patients as per normal practice.
- In case of any Serious Adverse Event (including medically important events and pregnancy outcome related events), the patient must be followed up until clinical recovery is complete and laboratory results have returned to normal, or until progression has been stabilized. This may imply that follow-up will continue after the patient has finished regular study schedule.

11.3 OBLIGATIONS OF MAH/MAH REPRESENTATIVE

During the course of the study, the MAH/MAH representative will report safety data to health authorities according to Directive 2001/83/EC and in accordance with all applicable local and global regulations (e.g., All serious ADR within 15 days [calendar] from the date of receipt of the reports to the health Authorities; and if required for some European countries all non-serious ADR within 90 days [calendar] from the date of receipt of the reports to the health Authorities).

12 PLANS FOR DISSEMINATING AND COMMUNICATING STUDY RESULTS

12.1 OWNERSHIP AND USE OF DATA AND STUDY RESULTS

No use of the data will be possible without the authorization of the MAH/MAH representative conducting the study.

12.2 PUBLICATIONS

MAH is responsible for presentations and/or publications. The study results must be submitted to MAH for review before publication.

The final decision to publish any manuscript/abstract/presentation will be made by the Genzyme. All manuscript/abstract/presentation must be submitted to MAH at least 45 calendar days in advance of submission. MAH may request that the MAH's name and/or names of one or several of its employees appear or do not appear in such publication. In order to allow competent authorities to review in advance the results and interpretations to be published, the marketing authorisation holder initiating, managing or financing a non-interventional PASS should communicate to the Agency and the competent authorities of the Member States in which the product is authorised the final manuscript of the article within two weeks after first acceptance for publication.

MAH can delay publication or communication for a limited time in order to protect the confidentiality or proprietary nature of any information contained therein.

14 APPENDICES

Appendix A Description of pregnancy outcomes

Each defect will be categorized using the CDC MACDP classification of birth defects (CDC MACDP, 1998). Major defects identified from the point of conception up to 1 year of age will be included in the analysis. Defects identified in any live birth will be considered in the primary analysis. Defects identified in any stillbirths or abortions (spontaneous or induced) will be considered in secondary analyses.

MACDP defines major structural or genetic birth defects as conditions that

- 1. result from a malformation, deformation, or disruption in one or more parts of the body, a chromosomal abnormality, or a known clinical syndrome;
- 2. are present at birth;
- 3. have a serious, adverse effect on health, development, or functional ability.

A **minor** structural defect is defined as a defect which occurs in less than 4 percent of the population but which has neither cosmetic nor functional significance to the child (e.g., complete 2,3 syndactyly of the toes).

Spontaneous abortion

Any loss of a fetus due to natural causes at \leq 20 weeks gestation determined from the estimated date of conception or by ultrasound as spontaneous abortion. If available, information from gross or pathological examination of the abortus or fetus will be documented.

Induced abortion

Pregnancy termination is defined as any induced or voluntary fetal loss. If available, information from gross or pathological examinations will be documented.

Preterm birth

A live birth that occurs before 37 completed weeks of gestation determined from the estimated date of conception. Elective caesarian deliveries or inductions prior to 37 completed weeks will be analyzed separately.

Small for gestational age

Birth size (weight, length, or head circumference) ≤10th percentile for gender and gestational age using the NCHS pediatric growth curves for full term infants. Prenatal growth curves will be used for preterm infants.

Property of the Sanofi Group - strictly confidential

Stillbirth

Any non-deliberate foetal death at >20 weeks gestation as estimated based on the estimated date of conception or by ultrasound.

Lost to follow-up

Enrolled women will be considered lost to follow-up if they are eligible, have provided informed consent, and have completed the initial intake interview but pregnancy outcome information is not available within 1 year of the estimated delivery date despite 4 attempts to obtain this information.

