7.2 RATIONALE

Given the prevalence of MS in women of childbearing age, a greater overall number of exposed pregnancies can be expected following regulatory approval and market penetration. It is not known if LEMTRADA could harm an unborn child. Therefore, the lack of sufficient human fetal safety data for LEMTRADA makes pregnancy outcome monitoring an important component of research on the safety of LEMTRADA.

The proposed registry utilizes an international, observational cohort design to evaluate rates of adverse pregnancy outcomes in women exposed to LEMTRADA during pregnancy. These rates will be compared with corresponding rates in unexposed external comparison groups (details defined in Section 4, under "Data sources") to assess if the risk of any observed adverse pregnancy outcomes in women exposed to LEMTRADA exceeds rates observed in unexposed external comparison groups. Women exposed to LEMTRADA during pregnancy are eligible to enroll provided their pregnancy is ongoing. Women with early prenatal testing are permitted into the study; statistical analysis will be adapted to detect potential impact of prenatal testing on the pregnancy outcomes.

16-Nov-2016 Version number: 1

Pharmacokinetic data on LEMTRADA suggests that LEMTRADA plasma concentrations become undetectable at 1 month post-treatment but effective contraceptive use is the primary recommendation when receiving a course of treatment with LEMTRADA and for 4 months following that course of treatment (a period >5 half-lives). Therefore, exposure inclusion criteria for this study dictate that participants in this registry are eligible if they were or become pregnant at any time from initiation of a course of treatment with LEMTRADA through the 4 months period following their last LEMTRADA infusion for that course of treatment.

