9.6.2 Data collected

9.6.2.1 Date collected from the mother (patient) by Health Care Provider (HCP)

Once patients sign the informed consent, patients' enrollment and follow up information are collected by the HCP. Whenever permitted in local legislation, signature of ICF will mean that the pregnant patient consents that medical records of herself and of the infant can be released by the HCP to the NC for further use in this Registry. After the ICF is signed, the enrolment interview can be done by HCP or registry staff if the HCP is not available; follow-up interviews can be done by phone or in person (by HCP or registry staff). Forms with patients' data completed by the HCP are sent to the National Coordinator by mail, fax, or email (on a secure server). Upon receipt, the National Coordinator reviews the forms for completeness, queries the HCP for missing data, and de-identifies and key-codes all forms before entering them into the CRF. Information to be collected during maternal interviews includes:

- Demographics: maternal age, maternal race/ethnicity (as per local regulations), education, family income category.
 - Of note: Patient race or ethnicity (e.g., "Caucasian/White, Black, Asian/Oriental, Others" will be collected in this study because these data are required by several regulatory authorities (e.g., on afro American population for Food and Drug Administration (FDA), on Japanese population for the PMDA in Japan, or on Chinese population for the CFDA in China)"
- Targeted medical history including prior treatment for MS.
- History of previous pregnancies and outcomes of each:
 - Pregnancy outcome: live birth, stillbirth, spontaneous abortion, induced abortion,
 - Pregnancy complications,
 - Fetal/neonatal abnormalities and type.
- Current pregnancy: fertility treatments (if applicable), date of last menstrual period, expected delivery date, prenatal tests conducted and results, pregnancy status.
- Risk factors: Smoking, alcohol use, illicit drug use, pre-pregnancy BMI
- LEMTRADA exposure (infusion dates).
- Concomitant medications including over-the-counter and prescription medications, vitamin supplements including folic acid, herbal medicines from one month prior to the date of enrollment.
- At pregnancy completion (as applicable depending on pregnancy outcome)
 - Pregnancy outcome (live birth, spontaneous abortion, stillbirth, induced abortion) and type (singleton or multiple),
 - For live births.

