- a) Gender, gestational age at delivery, mode of delivery, type/length of hospital stay, maternal and neonatal complications, maternal weight gain, presence or absence of major and minor structural defects, Apgar scores, birth weight, birth length, and head circumference.
- For other outcomes.
- a) Gestational age at time of event, pathology results if available, and presence or absence of major and minor structural defects. For stillborn infants gender, birth size, and autopsy results.
- Safety data
 - All SAEs including medically important events (see Section 11.1.1 for details),
 - All non-serious adverse events which per opinion of HCP/National Coordinator potentially have an impact on pregnancy outcomes.

At the conclusion of the pregnancy outcome interview, upon local practice, when local legislation requires this in addition to ICF signature, women can be mailed a packet with medical records release forms (or equivalent) from the pre- and postnatal HCP, the delivery hospital, and the pediatrician. Women will be asked to sign the medical records release forms and return the signed forms to the HCP(s). This process is to allow the National Coordinator to contact HCPs to confirm pregnancy outcomes and other above described data.

For retrospective cases, all data collections described above are applicable except that there would be no trimester interviews because the pregnancy outcome is already known.

Targeted follow-up

If a birth defect is noted, additional details regarding the birth defect may be requested from HCP by NC or by BDE to further define the etiology, facilitate classification, and to assess the presence of potential confounders of the birth defects. In addition, any specific questions the BDE (see Section 9.4) might have following initial review of the case will be included on the Targeted Follow-up Form.

The Targeted Follow-up Form collects the following from the reporter of the birth defect(s) or other appropriate HCP:

- Additional details of the birth defect (from initial report)
 - Assessment of etiology from HCP perspective
 - Requirement of surgical intervention to treat the birth defect (if so, dates and details)
- Potentially contributory factors
 - Medications or other products or agents taken during pregnancy
 - Maternal and paternal occupation
 - Concurrent medical/clinical conditions (occurring prior to and/or during pregnancy)
 - Any other factors that might have contributed to this outcome

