9.7.4 Analysis variables

Definitions of pregnancy outcomes are consistent with, but not limited to, definitions used by the Center for Disease Control and Prevention Metropolitan Atlanta Congenital Defects Program (CDC MACDP), the National Center for Health Statistics (NCHS), and Organization of Teratology Information Specialists (OTIS) (2,11). Overall pregnancy outcome will be classified into one of the following mutually exclusive categories: spontaneous abortions, induced abortions/elective terminations, stillbirth, preterm birth and live birth. Every birth defect identified in a live birth will be classified into major or minor congenital malformation.

Other outcomes of interest are: minor congenital malformations, preterm birth, small for gestational age at birth, and any other adverse pregnancy outcomes. The study will endeavor to assess all pregnancy outcomes for the presence of malformations and functional deficit in the infant up to 1 year of age. A detailed description of pregnancy outcomes is provided in Appendix A.

Additional analysis variables such as maternal age, smoking status during pregnancy, and maternal comorbidities may be included in analyses as important confounders or in subgroup analyses. These additional variables will be fully described in a separate statistical analysis plan which will be developed and finalized prior to database lock.

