9.7.5 Statistical methods

Endpoints are prospectively collected rates of spontaneous abortion, major and minor congenital malformations, stillbirth, elective terminations, preterm birth, small for gestational age at birth, and any other adverse pregnancy outcomes for women exposed to LEMTRADA during pregnancy.

All the comparisons below between women exposed to LEMTRADA during pregnancy (prospectively collected) and unexposed comparison groups will be carried out separately against each comparison group.

Rates and 95% CI will be calculated. Rates will be compared between women exposed to LEMTRADA during pregnancy (prospective) and women in unexposed comparison groups by calculating the relative risk (RR) and its 95% CIs. As the majority of the events rates are anticipated to be low, when applicable, comparisons will be conducted using exact statistical methods.

A supportive analysis of (prospective) spontaneous abortion as a time-to-event endpoint will be conducted using the Kaplan-Meier method adjusting for left-truncation. If data are available, propensity score matching and covariate adjustment may be used in the Cox regression context with left-truncation to adjust for potential confounding factors, such as gestational age at enrollment, comorbidities, prior birth defects/abnormalities, exposure to other medications, etc.

For other endpoints (prospective), if data are available, propensity score matching and covariate adjustment may also be used in the logistic regression context to adjust for potential confounding factors. These approaches will reduce the influence of risk modifiers in determining the event risk ratio between Lemtrada-exposed women and non-Lemtrada-exposed women.

Qualitative descriptive statistics on maternal and pregnancy characteristics and the timing of LEMTRADA exposure will be provided for the retrospectively collected pregnancy cases.

Additional supportive analyses will be documented in the statistical analysis plan (SAP).

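### Elective termination is compared by relative risk as one pooled class, with no reason for termination and no pregnancy intention listed for exposed women, so a raised ratio could not be clearly interpreted

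*Protocol*

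**What the plan says.** - **Endpoint.** Elective termination is a secondary outcome (Protocol section 8). Section 9.7.5 lists it among the endpoints: "stillbirth, elective terminations, preterm birth, small for gestational age at birth, and any other adverse pregnancy outcomes for women exposed to LEMTRADA during pregnancy". Exposed women are compared with "women in unexposed comparison groups by calculating the relative risk (RR) and its 95% CIs", separately for each comparison group. Section 9.7.4.2 also provides for this comparison.
- **Definition.** Appendix A reads: "Pregnancy termination is defined as any induced or voluntary fetal loss". Section 9.7.4 has a single class for it among the outcome categories: "spontaneous abortions, induced abortions/elective terminations, stillbirth, preterm birth and live birth".
- **Data on pregnancies not ending in live birth.** Section 9.6.2.1 lists "Gestational age at time of event, pathology results if available, and presence or absence of major and minor structural defects", and section 9.6.2.2 has the same items for verification. Neither section, nor the data schedule in Table 2 (section 9.6.1), names a reason or indication for termination.
- **Entry window.** Section 9.2.2.1 admits women pregnant at any time from the first infusion of a course to 4 months after its last. Section 7.2 says of that period that "effective contraceptive use is the primary recommendation when receiving a course of treatment with LEMTRADA and for 4 months following that course of treatment".
- **Pregnancy intention.** Section 9.7.4.3 lists unintended pregnancy among the comparison-cohort variables. The maternal interview list for exposed women in section 9.6.2.1 does not.

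**The concern.** A termination can follow a fetal anomaly, a maternal illness or a decision not to continue the pregnancy. The first two may carry safety information. The third depends largely on whether the pregnancy was wanted and on worry about drug exposure. Eligibility selects exposed women on conception in a window where contraception is recommended, and the protocol sets no such entry condition for Cohorts II and III. Terminations by choice could therefore be more frequent among exposed women with no biological effect.

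The pooled RR would then mix choice with indication. An excess could reflect intention only, and a real increase in medically indicated terminations could be hidden among the rest. Adjustment for intention is not available from the listed items, because intention is named on one side of the comparison only. A statistical analysis plan cannot recover an indication that was never recorded, so this has to be settled in the protocol and case report form.

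**Working it through.** **1. What the listed items can and cannot separate**

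| Type of termination | Items that help | What is missing |
|---|---|---|
| Fetal anomaly | Prenatal tests and results, structural defects, pathology if available, targeted follow-up once a defect is noted | A stated indication; pathology may be absent |
| Maternal illness | All serious adverse events, and non-serious events that may affect the outcome | A link between the event and the decision |
| By choice | None directly; inferred when nothing else is recorded | Reason, and pregnancy intention |

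Separation is possible in part. The by-choice group is a remainder, not a recorded category.

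**2. Check of the method on the protocol's own figure**

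Inputs from sections 9.5.1 and 9.5.2: exposed 204 × 0.95 = 193.8, stated as 193; comparator 125 × 0.96 × 0.98 = 117.6, stated as 117; one-sided Fisher exact test at 0.025; spontaneous abortion 13.5% with RR 2.0, that is 27.0% v 13.5%.

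Power = Σ over all pairs (x₁, x₂) of Bin(x₁; 193, p₁) × Bin(x₂; 117, p₂), counting pairs whose one-sided Fisher p-value is at most 0.025. This gives 78.1% against the stated 80%, and a normal-approximation cross-check gives 81.3%. The method reproduces the plan closely enough to use. That stated figure concerns spontaneous abortion; the protocol gives none for termination.

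**3. The same calculation for termination, on assumed rates**

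The whole excess is assumed to come from choice. RR = exposed rate / comparator rate.

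| Exposed v comparator (assumed) | RR | Chance of a one-sided 0.025 excess |
|---|---|---|
| 5% v 3% | 1.7 | 7% |
| 8% v 5% | 1.6 | 12% |
| 6% v 3% | 2.0 | 14% |
| 10% v 3% | 3.3 | 60% |
| 15% v 5% | 3.0 | 78% |

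**4. With medical indication held equal**

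Assume medically indicated terminations are 2% in both groups (true RR 1.0) and terminations by choice are 3% in the comparator, so the comparator total is 2% + 3% = 5%.

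| Choice, exposed | Pooled rates | Pooled RR | Chance of an excess |
|---|---|---|---|
| 3% | 5% v 5% | 1.0 | 1.3% |
| 5% | 7% v 5% | 1.4 | 6.5% |
| 8% | 10% v 5% | 2.0 | 28% |
| 10% | 12% v 5% | 2.4 | 49% |
| 15% | 17% v 5% | 3.4 | 89% |

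A difference in choice alone can thus give a pooled RR of 2 or more while the medically indicated RR is 1. The 0.025 level is borrowed from the sample-size section; section 9.7.5 fixes an RR with a 95% interval and no test for this endpoint.

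**The case against.** The case against is substantial, and much of it stands.

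- A reader might infer that the kinds of termination cannot be told apart at all. The protocol does not support that. It collects "prenatal tests conducted and results, pregnancy status", along with defects, pathology, gestational age and adverse events, and section 9.8.2 has outcomes verified by medical record review. Many anomaly cases and some illness cases could be identified. This stands.
- A reader might infer that an excess would be declared a LEMTRADA harm. No rule says so. The outcome is secondary, it is absent from the study-specific serious adverse event list in section 11.1.1, and section 9.7.5 permits propensity matching and covariate adjustment. This stands, although adjustment is conditional on available data and intention is not listed for exposed women.
- A reader might fear that surgical evacuation of a pregnancy already lost would be counted as induced. Appendix A defines spontaneous abortion by natural cause, which covers that case.
- It is not documented that comparison women conceived without contraceptive advice. Cohort II women may have used other MS medicines, and unintended pregnancy is recorded in both comparison cohorts. The direction of any imbalance is therefore plausible, not shown.
- The interview list is not worded as exhaustive, so the case report form may hold a reason item. The protocol does not require one.
- The rates are assumed, and modest gaps give only 7% to 14%. This stands, and the verdict carries the full range.

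**Conclusion.** The point holds in a limited form. The protocol fixes an RR for a pooled termination class, does not list the reason for termination, and lists pregnancy intention for the comparison cohorts only. The resulting RR would be hard to interpret, because a difference in intention could raise it without a drug effect.

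The size is unknown. It rests on termination rates that the protocol does not give, on the assumption that the whole excess is by choice, and on 193 v 117 women. Under those assumptions the chance of an apparent excess runs from about 7% to 78% across the pairs of rates tried. The documents do not support the stronger conclusions that separation is impossible or that an excess must be taken as harm. The primary outcome and the sample size are not affected.

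**What to change.** - **Sections 9.6.2.1 and 9.6.2.2:** add the reason for termination, with the options fetal anomaly, maternal or other fetal medical reason, non-medical, and not disclosed. In 9.6.2.1 also add pregnancy intention for exposed women, to match the comparison-cohort item.
- **Section 9.7.4.3:** seek the same reason item from the registry supplying Cohorts II and III.
- **Sections 9.7.4.2 and 9.7.5:** report terminations by indication. Give an RR for medically indicated termination only if the comparison registry holds the indication; otherwise describe it. State that the pooled RR is not to be interpreted on its own as a drug effect.

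The cost is two data fields and one split table. The question is sensitive, so some answers will be undisclosed. Medically indicated events will be few: at the assumed 2%, 193 × 0.02 ≈ 4 and 117 × 0.02 ≈ 2. Any formal comparison depends on what the other registry recorded, since its listed variables do not include the indication.
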